Cover Page for Study Protocol and Informed Voluntary Consent Form

Principal Investigator Name:	[name]
NCT Number:	Not yet
Official Title of Study:	Effects of Carbohydrate Counting Training Versus Standard
	Nutritional and Medical Therapy on Glycemic Control and
	Sarcopenia in Type 2 Diabetes: A Randomized Controlled
	Trial
Document Date:	March 24, 2022

Study Protocol

The Aim of the Study

The aim of this study to evaluate the effects of advanced carbohydrate counting training on anthropometric/body composition, biochemical, and clinical parameters of patients with type 2 diabetes mellitus who receive intensive insulin therapy. In addition, this study also evaluated the sarcopenia status of the patients and the effect of carbohydrate counting training on sarcopenia.

Study Design and Participants:

This study was planned as a randomized, controlled, 24-week study and was conducted with the voluntary participation of individuals with type 2 diabetes who were treated with intensive insulin. The study sample consisted of patients who received outpatient treatment at the Uskudar Diabetes Polyclinic of the Fatih Sultan Mehmet Training and Research Hospital Additional Service Building of the Ministry of Health of the Republic of Turkey between August 2022 and December 2024.

Inclusion criteria included, a history of type 2 diabetes mellitus or using insulin for more than one year, being over 18 years old, receiving basal and bolus insulin treatment, not having received carbohydrate counting training before, not receiving treatment with sulfanylurea drugs from oral anti-diabetics. Exclusion criteria included being pregnant or breastfeeding or planning a pregnancy during the study period, discontinuing insulin treatment during the study period, having active proliferative retinopathy, severe nephropathy, severe or newly diagnosed cardiac disease within 6 months or stage III–IV heart failure, having dementia or psychosis and cognitive impairment, receiving glucocorticoid treatment, being fed enterally or parenterally and receiving nutrition treatment due to another/concomitant disease, having end-stage renal or hepatic/ renal disease (other than proteinuria); having liver disease/microangiopathy diseases, having clinical cancer, chronic respiratory disease or amputations, or having any disease or condition that would prevent completion of the study.

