The study was conducted in accordance with the Declaration of Helsinki with the document number E-10840098-772.02-2030 and permission dated 24.03.2022 from the Istanbul Medipol University Non-Interventional Clinical Research Ethics Committee. Informed Voluntary Consent Form was obtained from all volunteers participating in the study.

Research Protocol

The training protocol, duration and content of each training session were decided by doctors and diabetes dietitians. Individual trainings on carbohydrate counting were organized for patients in the training group in 3 sessions on different dates in parallel with carbohydrate counting training levels. The first level training session (90 minutes), provided basic information on nutrition and health and comprised of topics as, macronutrients in food groups and their effect on plasma glucose, glycemic index, healthy food preferences and meal planning, carbohydrate contents in various food items, concept of carbohydrate change (portions of foods containing 15 grams of carbohydrate) were taught. In the second session (45 minutes), the patients calculated the carbohydrate contents of the meals they consumed based on the knowledge from the previous session. In addition, the meal plans, snacking and main meal frequencies, physical activities, effect of insulin doses on plasma glucose, noted down by each patient in their data sheets of each patient were reviewed. In the third training (45 minutes), calculation of the total carbohydrate content of the consumed meal were repeated, in order to reinforce the patient's training in this field. Furthermore, the patients were informed about the Insulin Correction Factor and Carbohydrate/Insulin ratios, and the insulin doses to be taken per meal were calculated and exemplified based on their meal plan data sheets.

Evaluation

A questionnaire form containing sociodemographic information was completed by face-to-face interview method. In addition, biochemical (HbA1c, fasting plasma glucose (FPG), C peptide, total cholesterol, HDL, LDL, triglyceride, estimated glomerular filtration rate) and anthropometric and body composition (weight-height, BMI, fat mass, fat ratio, muscle mass, lean tissue mass, waist circumference), hand grip strength, blood pressure and physical activity measurements of the patients were taken at the beginning, 12th week and 24th week of the study.

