#### **Statical Analysis Plan**

#### Sample Size, Randomization and Formation of Groups

A power analysis was conducted to determine the number of participants to be included in the study. In order to exceed the 80% power level, it was determined that the study should be conducted with 50 individuals (25 participants in the training and 25 participants in the control group), at a significance level was set at 5% with an effect size of 0.518 (df=41; t=1.683) [1].

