### **Statistical Analyses**

The statistical analysis of the data obtained from the study was evaluated using the IBM SPSS Statistics (version 22.0) package program. In order to evaluate the suitability of the data for normal distribution, One-Sample Kolmogorov-Smirnov test was conducted and kurtosis and skewness of the data was evaluated. Independent sample t-test was used to compare two independent groups among with normal distribution, dependent sample t-test and mixed design ANOVA were used to compare repeated measurements between two independent groups. All data have been provided with mean  $\pm$  standard deviation (mean $\pm$ SD). Mann-Whitney U test was used to compare data not showing normal distribution, and Wilcoxon test and Friedman test were used for repeated measurements between two groups. Categorical variables were compared using chi-square test and Fisher's exact chi-square test, and these data were shown with frequency (n, %) values. The significance level between the data was accepted as p=0.05. The graphical representations of the data were evaluated using the GraphPad Prism (version 9.3.0) package program.

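### For non-normal outcomes, the tests the SAP assigns to repeated measurements cannot compare the arms, and no between-arm comparison of change is named

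*SAP*

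**What the plan says.** The protocol (Study Design and Participants) describes the trial in these words: "This study was planned as a randomized, controlled, 24-week study". Under Evaluation, the biochemical, body-composition, grip-strength, blood-pressure and physical-activity measurements are "taken at the beginning, 12th week and 24th week of the study", so each has three values per patient. The SAP plans 25 patients per arm.

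The SAP's Statistical Analyses section assigns tests by distribution.

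- Normal, two groups: "Independent sample t-test was used to compare two independent groups among with normal distribution".
- Normal, repeated: "dependent sample t-test and mixed design ANOVA were used to compare repeated measurements between two independent groups".
- Non-normal, general: "Mann-Whitney U test was used to compare data not showing normal distribution".
- Non-normal, repeated: "Wilcoxon test and Friedman test were used for repeated measurements between two groups".

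Neither two-sample test is tied to a visit or to change from baseline. The section does not say which of these tests carries the efficacy conclusion, and the documents do not say which outcomes are expected to be non-normal.

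**The concern.** In a randomised trial the training effect is the difference between arms. Regression to the mean or closer monitoring can move both arms by the same amount, and a test of change within patients cannot separate that movement from an effect of training. The non-normal rule gives a between-group purpose to two tests that have no group term. A significant Wilcoxon or Friedman result could therefore be reported as a difference between groups when it shows only that values moved over time. This is a risk of misuse created by the wording, and the SAP does not state it as a decision rule.

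**Working it through.** **1. What each named test compares.**

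| Test in the SAP | Data type | Role given in the SAP | Contains an arm term? |
|---|---|---|---|
| Independent t | normal | two independent groups | yes |
| Dependent t | normal | repeated, two groups | no |
| Mixed design ANOVA | normal | repeated, two groups | yes (group-by-time) |
| Mann-Whitney U | non-normal | general comparison | yes |
| Wilcoxon (signed-rank) | non-normal | repeated, two groups | no |
| Friedman | non-normal | repeated, two groups | no |

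The normal repeated-measures row pairs one within-arm test with one test that does compare the arms. The non-normal repeated-measures row holds within-arm tests only.

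**2. Direct check.** For 50 simulated patients with three visits, 200 random reassignments of patients to the two arms gave one single Friedman p-value and one single signed-rank p-value. Neither test uses the arm label.

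**3. Size, if within-arm results were read as an effect.** The SAP states no such rule, so this is conditional. Let p be the probability that a within-arm test is significant. If both arms truly change by the same amount and the arms are independent, then

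P(significant in training only) = p(1 − p).

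This is largest at p = 0.5, where 0.5 × 0.5 = 0.25. That ceiling holds for any test, sample size or distribution. The table shows where it falls with 25 per arm, a two-sided 5% level and the paired t-test (exact noncentral t). The common change is in SDs of change and is assumed, because the documents give no value.

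| Common change (SD) | p | p(1 − p) |
|---|---|---|
| 0 | 0.050 | 0.048 |
| 0.2 | 0.161 | 0.135 |
| 0.4 | 0.484 | 0.250 |
| 0.6 | 0.821 | 0.147 |
| 0.8 | 0.970 | 0.029 |

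Simulation (20,000 runs per cell) gives the same pattern for the tests at issue. Signed-rank peaks at 0.249 near 0.4 SD with normal changes, and at 0.248 near 0.3 SD with heavy-tailed changes (t, 3 df). Friedman over three visits (within-patient correlation 0.5, heavy-tailed) peaks at 0.250 near 0.4 SD. The fall at large changes does not make the reading safer: it happens because both arms become significant. Mann-Whitney on change between arms rejects in 0.047 to 0.052 of trials in the normal and t (3 df) scenarios.

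**4. Which between-arm test.** Take the SAP's effect size of 0.518, read in SDs of the follow-up value, with 25 per arm, normal data, a two-sided 5% level and equal SDs at both visits. Let r be the baseline-to-follow-up correlation, which the documents do not give.

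- Follow-up value alone: effect 0.518, t-test power 0.43.
- Change from baseline: effect 0.518/√(2(1 − r)).
- Baseline-adjusted: effect approximately 0.518/√(1 − r²).

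| r | Change: effect, power | Baseline-adjusted: effect, approximate power |
|---|---|---|
| 0.3 | 0.438, 0.33 | 0.543, 0.47 |
| 0.5 | 0.518, 0.43 | 0.598, 0.54 |
| 0.7 | 0.669, 0.64 | 0.725, 0.71 |

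Change loses power against the follow-up value alone when r is below 0.5, since 2(1 − r) is then greater than 1. Mann-Whitney shows the same pattern in simulation: on change 0.31, 0.41 and 0.62 at these correlations, against 0.41 to 0.42 for follow-up alone. These are normal-theory figures, used only to rank the options. Power for skewed outcomes depends on the shape of the distribution.

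**The case against.** The strongest reply is that the sentence is loose English. The non-normal list mirrors the normal list: Mann-Whitney for the independent t-test, Wilcoxon for the dependent t-test, Friedman for repeated-measures ANOVA. The phrase about two groups may simply mean in each of the two groups. That reading is plausible and removes the mislabelling. It does not fill the gap, because Friedman replaces only the time part of mixed ANOVA and nothing in the non-normal list replaces the group-by-time term.

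It can also be said that Mann-Whitney is already named. It is, and it is valid, so a reader who infers that non-normal outcomes have no between-arm test at all goes beyond the text. What is missing is a statement of what Mann-Whitney compares: baseline, week 12, week 24 or change.

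A reader might infer that normal outcomes share the defect because the dependent t-test sits beside mixed ANOVA. They do not. Mixed ANOVA supplies the arm comparison, and the dependent t-test is a within-arm companion.

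A reader might also infer that the trial will claim efficacy from within-arm p-values and so carries a 25% false-positive rate. The SAP states no such rule, and 25% is the general ceiling of p(1 − p), not a property of this trial.

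Finally, no named endpoint can be shown to be affected, because the documents do not say which outcomes will be non-normal. That stands.

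**Conclusion.** The point holds for non-normal outcomes. As worded, the tests assigned to their repeated measurements cannot deliver the comparison that randomisation was meant to allow. Under the most charitable reading, no between-arm comparison of change is assigned to them. It should be fixed but is not fatal, because valid between-arm tests are named and mixed ANOVA covers normal outcomes. The size is conditional. If significance in the training arm only were taken as an effect, with independent arms and equal true change, the error could reach 25%. It is about 5% with no change and falls again for large changes. Mann-Whitney on change stays near 5%. How many outcomes are affected is unknown.

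**What to change.** In the SAP's Statistical Analyses section:

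- For non-normal outcomes, replace the Wilcoxon/Friedman rule with a between-arm test that uses baseline. This can be a rank-based baseline-adjusted comparison of the follow-up value, or Mann-Whitney on change from baseline. State the follow-up visit, and report an estimate with a 95% CI (Hodges-Lehmann for Mann-Whitney).
- For normal outcomes, keep the mixed ANOVA group-by-time term.
- Label the dependent t-test, Wilcoxon and Friedman as within-arm description.
- State that efficacy conclusions rest on the between-arm tests.

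The cost is SAP wording and a little syntax, using measurements the protocol already schedules. Within-arm significance can no longer be claimed as an effect. With normal data, change scores lose power against the follow-up value alone if the baseline-to-follow-up correlation is below 0.5. Baseline adjustment avoids that loss and had the higher approximate power at each correlation tried.

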Biochemical analyzes of the participants were performed in the Biochemistry Laboratory of Fatih Sultan Mehmet Training and Research Hospital. The individuals participating in the study were asked to give blood in the morning after 10-12 hours of fasting after dinner. Plasma glucose levels were analyzed by hexokinase method in colorimetricspectrophotometric Aeroset (Roche Hitachi cobas 6000) autoanalyzer and total cholesterol, HDL and triglyceride levels were analyzed by enzymatic colorimetric method. LDL levels were calculated using the Fridewald equation [1]. In addition, HbA1c levels were measured by high-performance liquid chromatography (HPLC) method. Serum C peptide levels were determined by Enzyme-Linked Immunosorbent Assay (ELISA) method (Roche Hitachi cobas 6000) using a commercial kit in an autoanalyzer.

Anthropometric measurements of the participants were taken by a dietician. The height of the participants was measured with a wall-type stadiometer with barefoot heels touching each other, arms hanging to the side, feet 45° apart and head in the Frankfort plan. Body weight and body composition were measured with TANITA BC-418MA bioelectrical impedance analyzer. BMI values of the participants were calculated based on weight and height measurement data. In waist circumference measurement, the midpoint between the

bottom of the rib bone and the iliac crest was determined and the circumference of this area was measured with a tape measure.

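### No primary outcome, visit or deciding between-group test is named for about 20 outcomes at p=0.05, and within-arm tests are listed for between-group comparisons

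*SAP*

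**What the plan says.** **Outcomes and visits.** The protocol's aim covers body measures, laboratory values and clinical measures, plus sarcopenia, without ranking them. Under Evaluation it lists biochemical, body-composition, grip-strength, blood-pressure and physical-activity measures and says that "measurements of the patients were taken at the beginning, 12th week and 24th week of the study". The timed walk test, height-adjusted muscle and nutrient intakes are described later in that section without a visit schedule.

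**Tests.** In the SAP's Statistical Analyses section the choice of test follows the type of data:
- Normal data: the independent-samples t-test for two groups; then "dependent sample t-test and mixed design ANOVA were used to compare repeated measurements between two independent groups".
- Non-normal data: "Mann-Whitney U test was used to compare data not showing normal distribution"; then "Wilcoxon test and Friedman test were used for repeated measurements between two groups".
- Categorical data: chi-square or Fisher's exact test.
- All data: "The significance level between the data was accepted as p=0.05".

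There is no outcome hierarchy, no multiplicity rule and no statement of which visit, test or ANOVA term decides the treatment effect.

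**Sample size.** The SAP justifies 25 per arm by an "effect size of 0.518 (df=41; t=1.683", attached to no outcome, visit or test. It cites a published trial for it.

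**The concern.** Two separate gaps meet here.

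First, with no designated comparison, any of about 20 outcomes at either follow-up visit can supply the result that is reported as the answer. A p-value just below 0.05 found that way is weak evidence, and a reader of a 50-patient trial could not tell whether it came from a planned question.

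Second, the paired t-test, Wilcoxon and Friedman tests compare time points within one set of patients. Because Mann-Whitney is named separately, Wilcoxon here must be the paired signed-rank test. The SAP lists all three for comparing repeated measurements between groups. If a significant change in the training arm and a non-significant one in the control arm were taken as a treatment effect, that conclusion could arise often when both arms change by the same amount.

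**Working it through.** **1. Does the sample-size paragraph identify the deciding test?** Inputs from the SAP: 25 per arm, 5%, more than 80% power, effect size 0.518, df=41, t=1.683.
- 1.683 is the one-sided 5% critical value of t at 41 df.
- A comparison of 25 with 25 has df = 25 + 25 − 2 = 48 and a two-sided critical value of 2.011. Its noncentrality is 0.518 × √(25/2) = 1.83, which gives power of 43% two-sided or 56% one-sided.
- A one-sided paired t-test on 25 patients has noncentrality 0.518 × √25 = 2.59 and power 80.8%, but its df is 24, not 41.

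The printed figures do not agree with any one of these tests, so the paragraph cannot stand in for a designated comparison.

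**2. How many outcomes?** From the protocol's Evaluation section:
- 8 biochemical + 7 body measures (weight, BMI, fat mass, fat ratio, muscle mass, lean mass, waist) + 4 others (grip, systolic and diastolic pressure, physical activity) = 19.
- Adding the timed walk test gives 20.
- Lower count: "LDL levels were calculated using the Fridewald equation" and "BMI values of the participants were calculated based on weight and height measurement data", so leaving out LDL and BMI gives 18; counting blood pressure once gives 17.
- Higher count: adding height-adjusted muscle and sarcopenia status to the 20 gives 22, before any nutrient intakes.

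**3. Chance of at least one false positive at one visit.** Assume that training affects none of the k outcomes and that each is tested once at two-sided 5%. If the tests are independent, the chance is 1 − 0.95^k: 58%, 64% and 68% for k = 17, 20 and 22. With a common pairwise correlation ρ it is

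1 − ∫ φ(c) [Φ((1.96 − √ρ·c)/√(1−ρ)) − Φ((−1.96 − √ρ·c)/√(1−ρ))]^k dc.

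| k | ρ=0.7 | ρ=0.5 | ρ=0.3 | ρ=0 |
|---|---|---|---|---|
| 17 | 27% | 39% | 49% | 58% |
| 20 | 29% | 42% | 54% | 64% |

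The documents give no correlations, so ρ is assumed. Testing at both follow-up visits raises the figures. For 20 outcomes and an assumed between-visit correlation of 0.7, simulation gives 60% at ρ=0.5 and 73% at ρ=0.3.

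**4. Within-arm results read as a treatment effect.** Let both arms of 25 change equally, and let p be the chance that one arm's within-arm test is significant for improvement. The chance that training is significant and control is not is about p(1 − p), which cannot exceed 0.5 × 0.5 = 25%. Simulated Wilcoxon tests on normally distributed changes gave:

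| Equal change in both arms (SD of change, assumed) | 0.2 | 0.3 | 0.4 | 0.5 |
|---|---|---|---|---|
| Significant in training only | 12% | 21% | 25% | 23% |

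The SAP uses Wilcoxon for non-normal data, so shape matters. At 0.2 SD the figure is about 3% for exponential changes with the long tail towards improvement, about 23% with the tail the other way, and about 20% for a t distribution with 3 df. With normal changes of 0.8 SD it falls below 5%. Over the shapes and sizes tried, the range was 0.1% to 26%; values just above 25% are simulation error. A between-group test at two-sided 5% errs in that direction 2.5% of the time.

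**The case against.** **Mann-Whitney is in the plan.** A reader might infer from the Wilcoxon and Friedman wording that non-normal data have no between-group test. The documents do not support that. The same sentence opens with Mann-Whitney, and under randomisation a comparison of week-24 values is a valid test of the treatment effect without change scores. What stands is that no visit is given and the test is not designated as deciding.

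**The mixed ANOVA is in the plan.** Its group-by-time term validly compares the arms for normal data. This also stands: the gap is one of designation, not of a missing method.

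**The wording may be loose.** A fair reading is Mann-Whitney between arms, and Wilcoxon and Friedman across visits within arms. A reader might infer that the investigators will judge efficacy on within-arm p-values, and might see support in the 80.8% for a one-sided paired test. Neither document says so, and the printed df does not fit that test with 25 patients. The harm is therefore conditional on how results are read, but the text leaves that reading open.

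**The outcomes overlap.** Weight, BMI, fat and lean measures are strongly related, so 64% is an upper figure and should not be quoted alone. The count is also approximate: the timed walk test may be what the protocol means by physical activity.

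**Conclusion.** The point holds as a gap in designation. About 20 outcomes at two follow-up visits are tested at 0.05 with nothing named as primary, and within-arm tests are described as serving between-group comparisons.

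At one visit the chance of at least one false positive is about 29% to 64%, depending on correlation, and it is higher over two visits. This assumes 20 outcomes, two-sided tests, a common correlation and no true effect on any of them. Even 17 outcomes at a correlation of 0.7 give 27%, more than five times the nominal 5%.

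The risk from within-arm reading runs from near 0% to about a quarter of trials, depending on the shape and size of the shared change. It arises only if those results are taken as evidence of a treatment effect. The plan does not lack valid between-group tests; it does not say which one counts, on what outcome, or when.

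**What to change.** 1. **Primary test.** Name one primary outcome and one visit. HbA1c at week 24 would fit the first-named subject of the title, although the aim lists body measures first; the sponsor should confirm. Test it once at two-sided 5% by ANCOVA with its baseline value as covariate. If the mixed ANOVA is kept instead, name its group-by-time term as the deciding test.
2. **Other continuous outcomes with a baseline.** Use a baseline-adjusted between-group model, transformed or rank-based if non-normal, or Mann-Whitney at a stated visit.
3. **Sarcopenia status.** Compare the arms at the same visit with the chi-square or Fisher test already in the SAP.
4. **Within-arm tests.** Keep the paired t, Wilcoxon and Friedman tests as description within each arm only.
5. **Reporting.** Present all non-primary outcomes as secondary with 95% confidence intervals, and make no confirmatory claim unless Holm-adjusted. State the visit schedule of the timed walk test.
6. **Timing.** The documents are in the past tense. If outcome data have been seen by arm, report these choices as post hoc.

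The cost is SAP wording, using data the protocol already schedules. Other nominally significant results become supportive only. If data have been seen, the primary test cannot be called pre-specified. The power gain of ANCOVA over group-by-time depends on the baseline correlation r, which the documents do not give. Assuming that 0.518 applies to final values, compound symmetry and the full effect by week 12, power is 54% against 45% at r=0.5, and 85% for both at r=0.8. The gain may therefore be nil, and naming the group-by-time term would be an acceptable remedy.
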